4.3.4 Contraception and Definition of Woman of Child-bearing Potential

4.3.4.1 Definition of Woman of Child-bearing Potential

- The Investigator or his or her designee, in consultation with the subject, will confirm that the subject has selected an appropriate method of contraception for the individual subject from the permitted list of contraception methods noted below and will confirm that the subject has been instructed in its consistent and correct use. At time points indicated in the Schedule of Assessments, the Investigator or designee will inform the subject of the need to use highly effective contraception consistently and correctly
- A woman is considered fertile following menarche and until becoming postmenopausal unless permanently sterile (see below)
- If fertility is unclear (e.g., amenorrhea in adolescents or athletes) and a menstrual cycle cannot be confirmed before the first dose of trial intervention, additional evaluation should be considered

Women in the following categories are not considered women of child-bearing potential (WOCBP):

1. Premenarchal
2. Premenopausal female with 1 of the following:
 - Documented hysterectomy
 - Documented bilateral salpingectomy
 - Documented bilateral oophorectomy

For individuals with permanent infertility due to an alternate medical cause other than the above, (e.g., Mullerian agenesis, androgen insensitivity), Investigator discretion should be applied to determining trial entry.

Note: Documentation for any of the above categories can come from the site personnel's review of the subject's medical records, medical examination, or medical history interview. The method of documentation should be recorded in the subject's medical record for the trial.

3. Postmenopausal female:
 - A postmenopausal state is defined as no menses for 12 months without an alternative medical cause
 - A high follicle-stimulating hormone (FSH) level in the postmenopausal range will be used to confirm a postmenopausal state in women who are less than 60 years old and not using hormonal contraception or HRT

4.3.4.2 Contraception Methods

Highly Effective Methods That Have Low User Dependency

- Implantable progestogen-only hormone contraception associated with inhibition of ovulation
- Intrauterine device (IUD)
- Intrauterine hormone-releasing system (IUS)
- Bilateral tubal occlusion
- Vasectomized partner. Vasectomized partner is a highly effective contraceptive method provided that the partner is the sole sexual partner of the WOCBP and the absence of sperm has

been confirmed. If not, an additional highly effective method of contraception should be used (e.g., male condom with spermicide). The spermatogenesis cycle is approximately 90 days

Highly Effective Methods That Are User-Dependent:

Combined (estrogen- and progestogen-containing) hormonal contraception associated with inhibition of ovulation:

- Oral
- Intravaginal
- Transdermal
- Injectable

Progestogen-only hormone contraception associated with inhibition of ovulation:

- Oral
- Injectable

Sexual abstinence

Sexual abstinence is considered a highly effective method only if defined as refraining from heterosexual intercourse during the entire period of risk associated with the trial intervention. The reliability of sexual abstinence needs to be evaluated in relation to the duration of the trial and the preferred and usual lifestyle of the subject.

5 Premature Discontinuation of Subjects or Trial

5.1 Subject Discontinuation

The subjects have the right to withdraw from the trial at any time and for any reason, without the need to justify their decision and without prejudice to their current or future medical care by the investigator or hospital.

If the reason for withdrawal is an AE, the AE should be reported and the subject should be followed up as outlined in the protocol.

Withdrawn subjects who have been dosed with the IMP must have an early termination (ET) visit performed as soon as possible after the dose for safety assessments. Regardless of the reason for withdrawal, the Investigator will make every effort to ensure an ET visit is performed for subjects who have been dosed with IMP.

The Investigator also has the right to discontinue subjects at any time based on the best interest of subjects.

Reasons for withdrawal from the trial:

- Withdrawal of consent
- Important protocol deviation that, in the opinion of the Investigator and after discussion with the Sponsor, may invalidate the trial results
- Investigator's decision for medical or safety reasons
- Pregnancy occurring between ICF signature and dosing
- Adverse events that might place the subject at unacceptable risk if participation is continued
- Subject is lost to follow-up
- The clinical trial is terminated by the Sponsor

A subject may be withdrawn if he/she develops an AESI such as hypotension, fluid overload, persistent abdominal pain, gall bladder, biliary and pancreatic disease of Grade 3 and above, according to the National Cancer Institute – Common Terminology Criteria for Adverse Events (NCI-CTCAE), version 5 [17].

Furthermore, during the trial liver toxicity will be closely monitored according to guidelines from the USA Food and Drug Administration (FDA) and subjects will be withdrawn from the trial if any of the following stopping criteria are met. Further enrolment and dosing will be interrupted if a single subject experiences documented liver function abnormalities that meet the following criteria (see also Section 10.10):

- ALT or AST $>8 \times$ ULN once
- ALT or AST $>5 \times$ ULN for more than 2 weeks
- ALT or AST $>3 \times$ ULN **and** total bilirubin $>2 \times$ ULN or INR >1.5
- ALT or AST $>3 \times$ ULN and clinical signs of fatigue, nausea, vomiting, right upper quadrant pain or tenderness, fever, rash, and/or eosinophilia ($>5\%$)

Study enrollment may potentially be resumed following the review of all available safety data by the investigator and Institutional Review Board/Independent Ethics Committee, with a concurrent/consensus opinion that the totality of the data suggests that this event is unlikely to be related to the study drug.

For all withdrawn subjects, site will attempt to perform EOT assessments matching the Day 14 visit at an ET Visit. The Investigator will document the date of discontinuation and, if possible, the main reason for the subject's withdrawal in the subject's medical record.

5.2 Subject Withdrawal of Consent and Subjects Considered Lost to Follow-up

Subjects who request to discontinue receipt of trial treatment will remain in the trial and must continue to be followed for protocol-specified follow-up procedures. The only exception to this is when a subject specifically withdraws consent for any further contact with him or her or persons previously authorized by the subject to provide this information. The withdrawal of consent should be explained in detail in the medical records by the Investigator, as to whether the withdrawal is only from further receipt of IMP or also from trial procedures and/or posttreatment trial follow-up, and entered on the appropriate case report form page.

All reasonable efforts must be made to locate withdrawn subjects to determine and report their ongoing status. This includes follow-up with persons authorized by the subject as noted above. All attempts should be documented in the subject's medical record. For subject who are lost to follow-up (e.g., have not completed the trial, but cannot be reached), the site will use legally permissible methods to determine if the subject has died and to obtain the date and cause of death (for example, through use of public domain information or a release signed by the family to obtain health records). If the Investigator uses a third-party representative to assist in the follow-up portion of the trial and that has been included in the subject's informed consent, the Investigator may use those means to access follow-up. The Investigator can also use other public vital status data necessary to complete the follow-up portion of the trial if necessary. If after all attempts, the subject remains lost to follow-up, then the last-known-alive date, as determined by the Investigator, should be reported and documented in the subject's medical record.

Subject's may withdraw from the trial at any time at their own request, or they may be withdrawn at any time at the discretion of the Investigator or Sponsor for safety, as noted in the protocol or for behavioral reasons, or the inability of the subject to comply with the protocol-required schedule of trial visits or procedures at a given Investigator site. The ET visit applies only to subjects who are randomized and then are prematurely withdrawn from the trial.

It may be appropriate for the subject to return to the clinic for final safety assessments to be scheduled as early as feasible following the decision to withdraw from the trial.

Lack of completion of all or any of the withdrawal/early termination procedures will not be viewed as a protocol deviation so long as subject safety was preserved.

If the subject withdraws from the trial and also withdraws consent for disclosure of future information, no further evaluations should be performed, and no additional data should be collected. The Sponsor may retain and continue to use any data collected before such withdrawal of consent.

Subjects who withdraw from the trial may be replaced at the discretion of the Investigator upon discussion with the Sponsor.

5.3 Trial Termination

If the Investigator, the Sponsor, or the Safety Medical Monitor (who reviews medical information and safety data, and consults with the site on eligibility criteria) becomes aware of conditions or events that suggest a possible hazard to subjects if the trial continues, the trial may be terminated after appropriate consultation between the relevant parties. The trial may also be terminated early at the Sponsor's discretion in the absence of such a finding.

Conditions that may warrant termination include, but are not limited to:

- The discovery of an unexpected, significant or unacceptable risk to the subjects enrolled in the trial
- Failure of the site to enroll subjects at an acceptable rate
- A decision on the part of the Sponsor to suspend or discontinue development of the drug
- The site cannot comply with the requirements of the protocol
- It is not possible for the site to comply with GCP standards
- IRB or a regulatory decision
- Enrollment and further dosing of new subjects will be interrupted if two or more subjects experience any of the AESIs mentioned in Section 5.1. of moderate intensity (NCI-CTCAE Grade 3) and/or if one or more subjects experience a Grade 4 event (unless clearly not attributable to the study drug)

6 Investigational Medicinal Product and Concomitant Medications

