9.4.4 Liability and Insurance

The Sponsor will cover this trial by means of an adequate insurance of the participating subjects which will be in place prior to the start of the trial.

As per local regulations, details about the insurance are described in the subject information sheet and ICF. A copy of the insurance statement is filed in the Investigator Site File and the subject can request a copy.

9.5 Reporting of Safety Concerns and Serious Breaches of the Protocol or ICH GCP

In the event of any prohibition or restriction imposed (i.e., clinical hold) by an applicable regulatory authority in any area of the world, or if the Investigator is aware of any new information that might influence the evaluation of the benefits and risks of the IMP, Sponsor immediately of any urgent safety measures taken by the Investigator to protect the trial subjects against any immediate hazard, and of any serious breaches of this protocol and/or of ICH GCP that the Investigator has become aware.

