10.2 Definition and Assessment of (Serious) Adverse Events and Other Safety Related Events

An AE is any untoward medical occurrence in a subject or a clinical investigation subject administered a pharmaceutical product, and which does not necessarily have a causal relationship with the trial procedure. An AE can therefore be any unfavorable and unintended sign (including an abnormal laboratory finding), symptom, or disease temporally associated with the use of an IMP, whether or not related to the IMP [1]. Medical conditions present at the initial trial visit that do not worsen in severity or frequency during the trial are defined as baseline medical conditions (medical history) and are not to be considered AEs.

The sources of AEs include:

- The subject's response to questions about his/her health (a standard nonleading question such as "How have you been feeling since your last visit?" is asked at each visit)
- Symptoms spontaneously reported by the subject
- Investigations and examinations with findings that are assessed by the Investigator to be clinically significant
- Other information relating to the subject's health becoming known to the Investigator

For surgical or diagnostic procedures, the condition/illness leading to such a procedure is considered as the AE rather than the procedure itself.

Specific information related to liver safety can be found in Section [10.10](#).

An SAE is classified as any untoward medical occurrence that:

- Results in death
- Is life-threatening
- Requires in-patient hospitalization or prolongation of existing hospitalization
- Results in persistent or significant disability/incapacity
- Is a congenital anomaly/birth defect in a neonate/infant born to a mother exposed to apraglutide (also applies if father was exposed to apraglutide)
- Is a medically significant event in the Investigator's judgment (e.g., may jeopardize the subject or may require medical/surgical intervention to prevent one of the outcomes listed above) [27]

Events that Do Not Meet the Definition of an SAE:

- Elective hospitalizations to administer, or to simplify trial treatment or trial procedures are not considered SAEs. However, all events leading to unplanned hospitalizations or unplanned prolongation of an elective hospitalization (for example, undesirable effects of any administered treatment) must be documented and reported as SAEs
- Hospitalization or prolongation of hospitalization as part of a routine procedure

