- Hospitalization for a survey visit, annual physicals or social reasons
- Hospitalization that does not include an overnight stay
- Elective hospitalizations for pre-existing conditions documented in the medical history that have not worsened
- Hospitalization to facilitate treatment of disease/illness with other treatment options, although these treatments are not permitted as per the protocol and will be documented as a protocol deviation

In case of doubt, an event should be reported within timelines.

Definition of Adverse Events of Special Interest

An AESI, serious or non-serious, is an AE of scientific and medical concern specific to the Sponsor's product or program, for which ongoing monitoring, additional information, and rapid communication by the Investigator to the Sponsor can be appropriate. Depending on the nature of the event, rapid communication by the trial Sponsor to other parties (e.g., regulators) might also be warranted in line with Council for International Organizations of Medical Sciences standards and local regulations.

The following are considered AESIs for this trial:

- Injection site reactions (ISR)
- Gallbladder, biliary, and pancreatic disease
- Fluid overload
- Hypotension
- Persistent abdominal pain

Injection site reactions

Subjects will be monitored for ISRs for at least 1 hour after IMP administration given at site, until the reaction stops. The individual symptoms of the ISR (e.g., injection site pain, injection site pruritus

[itching], injection site erythema [redness], injection site edema [swelling], injection site bruising) should be reported as AEs.

Data on local tolerability will be collected as an AESI. The following characteristics of ISRs will be documented:

- Pain
- Erythema
- Induration
- Pruritus
- Bruising

Severity and duration of these features of the ISR will be collected by the site by direct observation when IMP is administered on site. When IMP is administered at home, ISRs should be reported to the site for documentation in the subject's source documents and entry into the eCRF.

Gallbladder, Biliary and Pancreatic Disease

These should be monitored by symptoms, liver enzymes (ALT, AST, alkaline phosphatase), bilirubin, lipase, and amylase and subjects should be treated according to the Investigator's judgement.

Fluid Overload, Hypotension and Persistent Abdominal Pain

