10.3 Safety Reporting

10.3.1 Reporting of Adverse Events

All AEs must be reported to the CRO through the eCRF and within the data entry timeline defined for this trial and stipulated in the clinical trial agreement.

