10.3.2 Reporting of Adverse Events of Special Interest

All AESIs must be reported to the CRO through the eCRF and within two weeks following the event.

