10.3.3 Reporting of Serious Adverse Events

All SAEs must be reported immediately and within a maximum of 24 hours to the CRO and thereafter the CRO will report to the Sponsor of the trial.

Serious adverse event primary information should be collected through the eCRF and the reporting is done via paper form, which can be submitted via email or fax to PRA Safety.

The contact information is:

- North/South America
- Fax: [REDACTED]
- Email: [REDACTED]

The Sponsor/CRO will re-evaluate the SAE and return the form to the site, requesting clarification or follow-up information if needed. After the initial SAE report, the Investigator is required, proactively, to provide further information regarding the subject's condition.

Serious AEs resulting in death will be reported to the IRB within 7 days.

The minimum data required for a report is:

- Subject identifier (ID)
- Trial ID
- Date of enrolment
- Date and time of start of SAE
- Description of SAE
- Severity of SAE
- Assessment of causality relationship to IMP
- Name and contact details of person reporting the event

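### The two-subject dosing halt in Protocol 5.3 relies on AESI reports that 10.3.2 allows to take two weeks, with no required relay between the two sites, so non-serious Grade 3 events may be counted late

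*Protocol*

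**What the plan says.** **The halt.** Protocol 5.3 states: "Enrollment and further dosing of new subjects will be interrupted if two or more subjects experience any of the AESIs mentioned in Section 5.1". The grade for this limb is CTCAE Grade 3, which the text also labels moderate. A single Grade 4 event triggers the halt as well. The bullet ends with an exemption for events clearly not due to study drug. The AESIs named in 5.1 are hypotension, fluid overload, persistent abdominal pain, and gallbladder, biliary and pancreatic disease. Injection site reactions are AESIs under 10.2 but are not named in 5.1, so they do not count. The synopsis lists two trial sites.

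**The reporting clocks.** For AESIs, 10.3.2 says: "All AESIs must be reported to the CRO through the eCRF and within two weeks following the event". Under 10.2 an AESI may be serious or non-serious. SAEs go by a faster route in 10.3.3: "within a maximum of 24 hours to the CRO and thereafter the CRO will report to the Sponsor of the trial". For AEs generally, 10.3.1 says "All AEs must be reported to the CRO through the eCRF and within the data entry timeline defined for this trial", and that timeline is set in the clinical trial agreement.

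**The count.** Section 5.3 describes a Safety Medical Monitor who reviews safety data. It does not say who keeps the count or how quickly the sites are told.

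**The concern.** The halt protects subjects who have not yet been dosed. It works only if someone learns of the second qualifying event in time to stop the next injection, at either site. A two-week reporting allowance does not fit a rule that acts on the second event. Two sites that both follow 10.3.2 could keep dosing after the halt condition is met, because nobody yet holds both reports. Neither would be in breach. At stake is the exposure of a small number of further subjects. The PK comparison is not at stake.

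**Working it through.** The plan gives no figure to reproduce here: no dosing pace, no event rate and no power calculation. The check is a timeline, a reading of the other channels and an illustration.

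**1. Timeline.** Let two qualifying non-serious Grade 3 AESIs occur on days t1 ≤ t2. The halt condition is met on t2. Reports are due at the CRO by t1 + 14 and t2 + 14, so the latest compliant day on which the CRO holds both is t2 + 14.

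| Days between events | Condition met (day) | CRO holds both by (day) | Lag (days) |
|---|---|---|---|
| 0 | 0 | 14 | 14 |
| 3 | 3 | 17 | 14 |
| 7 | 7 | 21 | 14 |
| 14 | 14 | 28 | 14 |
| 30 | 30 | 44 | 14 |

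The lag does not depend on the spacing. Any time from CRO to Sponsor and from Sponsor to site comes on top, and no limit is stated for either. On the 24-hour route the reporting step would take 1 day instead of 14.

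**2. Which site is exposed.**
- Both events at one site: that Investigator can stop at once. The other site need not be told.
- One event at each site, first not relayed: neither site knows the condition is met.
- One event at each site, first already relayed: the site seeing the second event can stop at once. The other may not learn of it until t2 + 14 or later.

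In each case the main exposure is at the site that did not see the second event.

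**3. Other channels.**
- 10.2, seriousness: a Grade 3 AESI is an SAE, on the 24-hour clock, if it is medically significant or "Requires in-patient hospitalization or prolongation of existing hospitalization". Also, "In case of doubt, an event should be reported within timelines". This removes many events, but not one judged non-serious.
- 10.2, AESI definition: "rapid communication by the Investigator to the Sponsor can be appropriate". This is permissive and sets no time.
- 7.3.9: the Safety Medical Monitor should be told of clinically significant trial-related abnormalities at Day 8 discharge. Events that resolve earlier or start later are not covered.
- 8.4: safety data are reviewed as the trial runs, with no interval stated.
- 9.5: the Investigator who is "aware of any new information that might influence the evaluation of the benefits and risks of the IMP, Sponsor immediately" appears meant to notify the Sponsor at once. The sentence lacks its verb, and the other site is not mentioned.
- 10.3.4: the Sponsor informs Investigators of SUSARs, as necessary. Those are serious events.
- 10.3.1: the agreement may set a shorter entry timeline. It is not among the documents.

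None sets a shorter limit for every non-serious Grade 3 AESI, and none requires notice to the other site.

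**4. Illustrative doses.** Inputs: about 16 subjects in Part 1 (3.1.1); first visit November 2020 and last visit March 2021 (synopsis). Assumption: even dosing over a window of W days, so doses in 14 days = 16 × 14 / W.
- Full calendar span, 1 November to 31 March: W = 150, giving 224/150 = 1.5.
- Less 28 days of screening and 14 of follow-up: W = 108, giving 224/108 = 2.1.
- Shortest case, 30 November to 1 March (91 days), less 28 for screening and 15 for follow-up: W = 48, about 7 weeks, giving 16/7 × 2 = 4.6 (4.7 with 48 days unrounded).

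With a 1-day lag the same windows give 16/150 = 0.1 to 16/49 = 0.3 doses.

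Dosing will not be even. Under 3.1.1 the severe group is recruited first, and controls follow once its mean age and weight are known. Clustered dosing would raise the count and a pause between cohorts would lower it.

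**The case against.** The strongest reply is that little is left to fix. Subjects are confined until Day 8, and an event that matters clinically would usually meet an SAE criterion and be reported within 24 hours. AESIs are also AEs, so an unseen contractual timeline may already be shorter than two weeks. A Safety Medical Monitor reviews safety data. The single 5 mg dose is far below the 56.9 mg reported as well tolerated. All of this stands, and it makes the gap narrow. It does not close it: each protocol channel is conditional, permissive or without a time limit, and the agreement cannot be relied on unseen. The halt was written for the unlikely case.

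A reader might also infer more than the documents support:
- **That 14 days is the longest possible delay.** It bounds only the report to the CRO; the later steps have no stated limit.
- **That events two weeks apart leave no delay.** That requires the first report to have been relayed, and even then it holds only at the site seeing the second event.
- **That 1.5 to 4.6 subjects would be dosed in error.** The range rests on assumed even dosing, and its upper end on the shortest window the dates allow.
- **That every Grade 3 AESI waits two weeks.** Those judged serious do not.

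**Conclusion.** The point holds, in a limited form. For Grade 3 AESIs judged non-serious, the protocol requires a halt on a cross-site count but does not require the information to arrive or be shared in time. The reporting step alone may compliantly take 14 days after the second event. Total delay has no stated limit. It will be shorter if any of the channels above operates promptly.

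The cost in extra doses cannot be sized from the documents, and the range given is an illustration. Two such events are unlikely on the tolerability described, although no event rate is stated. The primary PK result is unaffected. The change is worth making because it concerns a mandatory safeguard and is cheap.

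Two related ambiguities affect what is counted. Section 5.3 calls Grade 3 moderate, while 10.6 defines moderate on a separate functional scale alongside NCI-CTCAE grading, and 5.1 speaks of Grade 3 and above. It is also unclear whether the exemption for events clearly not due to study drug covers both limbs of the halt or only Grade 4.

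**What to change.** **In 10.3.2:** require any Section 5.1 AESI of CTCAE Grade 3 or higher, and any Grade 4 event, serious or not, to be reported within 24 hours of awareness by the 10.3.3 route to the CRO and the Safety Medical Monitor. The Safety Medical Monitor keeps the 5.3 count and notifies both sites the same day. Keep two weeks for all other AESIs. Grade 4 events are included because the Grade 4 limb of 5.3 is not expressly confined to AESIs.

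**In 5.3:** replace the moderate-intensity wording with NCI-CTCAE Grade 3 or higher, and state whether the attribution exemption applies to both limbs.

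**Cost:** short wording changes in two sections, plus faster reporting and same-day relay for what should be a few events. The 24-hour route and the Safety Medical Monitor role already exist.
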